**Rapid testing for infectious diseases.** Upon enrollment, participants will provide 2 finger stick whole blood samples for rapid testing of HIV and HCV at baseline, 3-months, and 6-month follow up. Participants enrolled in the intervention between February 1, 2023 and March 31, 2023 will complete the baseline and 3-month rapid testing only. Vivent Health prevention staff are trained to perform point-of-care tests for these infections using the Alere Determine™ HIV-1/2 Ag/AB Combo (Alere Inc., Waltham, MA) and the OraQuick® HCV Rapid Antibody Test (OraSure Technologies, Bethlehem, PA). During the 20 minutes while awaiting test results, participants may complete the ACASI questionnaire (described above). If testing by appointment, participants should complete the survey before arriving to their appointment. If both rapid tests are non-reactive, then the study visit will end for non-intervention clients and an appointment will be made for their 3-month visit. Among intervention clients, the study visit will end and an appointment will be made for intervention visit or phone/video call. If either of the 2 rapid tests are reactive, then SSP staff will perform venipuncture to collect a blood specimen to be sent to the Wisconsin State Laboratory of Hygiene (WSLH) for confirmatory testing, and arrange a follow-up visit to review confirmatory test results and provide linkage to care, if needed. In the event that a participant cannot provide a blood specimen for confirmatory testing due to poor venous access, they will be invited to return at a later date for another blood draw attempt. Those confirmed to have active HIV or HCV infection will be linked to a local provider with the assistance of a Vivent Health case manager or Prevention Navigator.

The test results and risk data collected on the HCV and HIV test forms will be entered into Vivent Health's standard of practice database, ServicePoint. Study ID numbers will be included to identify the results as study participants. ServicePoint will securely send data to WEDSS regularly. Only those on the HCV team at WI DHS, which consists of three research team members, will have access to the data. Test forms will be securely faxed to UW-Madison and mailed to DHS, then securely locked at Vivent Health, UW-Madison, and DHS.

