In the past 3 months, have you gotten buprenorphine shots – like Sublocade – from a doctor or program?	Intermediate Client-level	ACASI Survey	Change in frequency	✓ T 0 , T 1 , T 2

If I wanted to start medical treatment for opioid or heroin addiction, I could easily get buprenorphine or Suboxone or Subutex.	Short-term Client-level	ACASI survey	Change in Likert-scale	T 0 , T 1 , T 2
If I wanted to start a medical treatment for opioid or heroin addiction, I could easily get into a methadone program	Short-term Client-level	ACASI survey	Change in Likert-scale	T 0 , T 1 , T 2
Any outpatient visit for MAT for opioid use disorder post initiation of CCPH or control	Intermediate Client-level	Medicaid	Change in frequency	✓ T -2 , T 0 , T 2
Prescription fill for methadone, buprenorphine, naltrexone, probuphine post initiation of CCPH or control	Long-term community-level	Medicaid	Change in frequency	✓ T -2 , T 0 , T 2
Treatment for hepatitis C				
Utilization of HCV treatment among participants	Intermediate Client-level	Medicaid	Change in rate of HCV treatment	✓ T 0 , T 1 , T 2
Successful HCV treatment among participants	Long-term Client-level	WEDSS	Change in cure rate of HCV treatment	T -4 , T 0 , T 4
Decrease in prevalence of HCV	Long-term County-level	WEDSS	Change in rate of HCV by county	T -4 , T 0 , T 4
Do you currently have health insurance or health care coverage?	Short-term Client-level	ACASI Survey	Change in rate of health insurance	T 0 , T 1 , T 2
If I ever tested positive for hepatitis C, I'm confident I could get linked to a medical expert and start hepatitis C treatment.	Short-term Client-level	ACASI Survey	Change in Likert-scale	T 0 , T 1 , T 2
Number of appointments made for HCV treatment	Short-term Client Level	CCPH Program data	Change in frequency	T 0 , T 1 , T 2
Prescription fill for DAAs post initiation of CCPH or control	Intermediate Client-level	Medicaid	Change in frequency	✓ T -2 , T 0 , T 2
Lower risk of viral hepatitis				

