HIV prevalence	Long-term County-level	WEDSS	Change in rate of HIV incidence	T -4 , T 0 , T 4
Lower risk of drug overdose				
If I wanted the overdose reversal drug naloxone or Narcan, I could easily get it.	Short-term Client-level	ACASI survey	Change in Likert-scale	T 0 , T 1 , T 2
Narcan distribution	Intermediate County-level	Lifepoint	Change in narcan distribution	T -2 , T 0 , T 2
Overdose hospitalizations	Long-term County-level	Wisconsin Hospital Administration Data	Change in rate of overdose-related hospitalizations	T -4 , T 0 , T 4

Probable opioid overdose	Long-term County-level	Wisconsin Ambulatory Run Data System	Change in rate of overdose-related ambulatory run	T -4 , T 0 , T 4
Overdose death	Long-term County-level	Wisconsin Mortality data	Change in rate of overdose-related death	T -4 , T 0 , T 4
Smoking cessation				
Quit-line encounters	Short-term Community-level	Quit-line database	Change in number of quit-line uses	T -4 , T 0 , T 4
Do you smoke cigarettes?	Intermediate Client-level	ACASI Survey	Change in prevalence	T 0 , T 1 , T 2
On average, how many cigarettes do you smoke a day?	Intermediate Client-level	ACASI Survey	Change in median number of cigarettes	T 0 , T 1 , T 2
Overall smoking prevalence by county	Long-term County-level	BRFSS	Change in prevalence	T -4 , T 0 , T 4
Self-stigma				
How much do you feel ashamed of using drugs?	Intermediate Client-level	ACASI Survey	Change in Likert- scale	T 0 , T 1 , T 2
How much do you feel people avoid you because you use drugs?	Intermediate Client-level	ACASI Survey	Change in Likert- scale	T 0 , T 1 , T 2
How much do you fear you will lose your friends because you use drugs?	Intermediate Client-level	ACASI Survey	Change in Likert- scale	T 0 , T 1 , T 2
How much do you fear family will reject you because you use drugs?	Intermediate Client-level	ACASI Survey	Change in Likert- scale	T 0 , T 1 , T 2

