How much do you think other people are uncomfortable being around you because you use drugs?	Intermediate Client-level	ACASI Survey	Change in Likert- scale	T 0 , T 1 , T 2

\*Data sources used to measure the effectiveness of intervention include:

ACASI Survey: the harmonized survey used in the UG3 phase

WEDSS: Wisconsin Electronic Disease Surveillance System

Medicaid: Wisconsin Medicaid Program

IQVIA: Purchased prescriber data

WIR: Wisconsin Immunization registry

Lifepoint: Syringe service program database of needle exchange encounters and narcan distribution

BRFSS: Behavioral Risk Factor Surveillance System

SAMHSA: Database of DATA-Waived Practitioners

\*Time is measured in 3-month intervals based on the intervention assessment phases

T-4 a year prior to the intervention

T-2 6 months prior to the intervention

T0 Start of the intervention

T1 3 month follow up

T2 6 month follow up

T4 12 month after intervention

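### The county WEDSS rates for HCV and HIV in Appendix 2 are partly produced by the study's own testing and cannot show whether the programme changed infection

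*Combined protocol and SAP*

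**What the plan says.** Section 6.0 (Aim 3) names no single primary outcome and refers to Appendix 2 for what will be measured. Two of the roughly 50 rows there concern how often infection occurs at county level, with WEDSS as source:

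- HCV: "Decrease in prevalence of HCV", measured as "Change in rate of HCV by county".
- HIV: a row named as prevalence but measured as "Change in rate of HIV incidence".

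Both are taken at T-4 (a year before), T0 (start) and T4, which is defined only as "12 month after intervention". Section 3.0 describes a framework for comparing served with unserved counties.

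The study also supplies data to WEDSS. Section 5.4 states that "participants will provide 2 finger stick whole blood samples for rapid testing of HIV and HCV at baseline, 3-months, and 6-month follow up". Results are entered in the agency's database, and "ServicePoint will securely send data to WEDSS regularly". The state laboratory separately reports its confirmatory results to state surveillance. On the same results, "Study ID numbers will be included to identify the results as study participants".

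Appendix 1, section 1.6 plans 270 participants at intervention sites and 135 across the control sites. Section 5.1 had already placed HIV and HCV testing at all six sites in UG3. No text separates study-generated reports from the county counts, plans a count of tests done, or uses participants' own results for new HIV or HCV infection.

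**The concern.** A rate of reported cases depends on how many people are tested as well as how many are infected. A positive first found at a study visit, mostly infection that was already there, enters the county count as a case. UH3 testing therefore pushes the later rate up. It does so more at intervention sites, which test about twice as many people, unless their counties also hold about twice the population. UG3 testing may have raised the year-before value, which pushes a before/after comparison the other way.

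At stake is any statement about HCV or HIV occurrence drawn from these rows, in either direction. Aim 3's main target, receipt of services, does not depend on them.

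**Working it through.** **The plan's own figure.** Section 7.0 states 80% power for 28% against 42% with 270 and 135 participants. A two-sided 5% test of two proportions (sidedness and alpha assumed) gives 0.794, so the figure reproduces. It concerns perceived access to services. No power is stated for the county rows.

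**Inputs from the documents.** 270 and 135 participants; three test visits; 241 RNA-positive people in the targeted catchments in 2016-17, and about 15% of reported HCV cases passing through the state laboratory (section 5.2.1); 991 UG3 participants in the linkage (section 5.1.1).

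**Assumed inputs.** First-report yield p of 5-20%; 40-60% of participants susceptible to HCV; incidence of 5-25 per 100 person-years; navigation halving incidence for six months; equal county populations; all participants living in the six counties; every first report falling in the T4 year.

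1. *People tested.* 270/135 = 2.0. Visits are at most 270 × 3 = 810 against 135 × 3 = 405, but repeat tests of known positives should add no cases, so headcount is what matters.

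2. *From counts to rates.* If R is the ratio of intervention to control population, the relative push on the rate is 2/R: 4.0 at R = 0.5, 2.0 at R = 1, 1.33 at R = 1.5 and 1.0 at R = 2. The between-group distortion vanishes at R = 2. The upward push within intervention counties remains at any R.

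3. *Between-group excess.* 270p − 135p = 135p. At 5%: 13.5 − 6.75 = 6.75. At 20%: 54 − 27 = 27.

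4. *True benefit.* Low: 270 × 0.5 year × 0.4 × 0.05 × 0.5 = 1.35 infections prevented. High: 270 × 0.5 × 0.6 × 0.25 × 0.5 = 10.1.

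5. *Sampling noise.* Background for three counties: 241/0.15/2/2 = 402 a year if the 15% share applies to these catchments, or 241/4 = 60 a year using only the laboratory's RNA-positive cases. For a difference-in-differences of four Poisson counts, the 95% half-width is 1.96 × √(4 × 402) = 79 or 1.96 × √(4 × 60.25) = 30. Both the 7-27 excess and the 1-10 benefit lie inside it. The excess would pass the half-width only at p = 30.4/135 = 22.5% on the small background, or 78.6/135 = 58% on the large one.

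6. *UG3.* At the same yield, 991 × 0.05 = 50 to 991 × 0.20 = 198 first reports, or 25 to 99 per three counties on an even split. An even contribution cancels between groups. Before/after in the intervention counties it opposes the 13.5 to 54 that UH3 adds, and how much falls in the T-4 window is unknown. The noise result in step 5 therefore covers the between-group comparison; before/after, the sign itself is open.

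7. *Does the sign reverse?* With step 4's benefit, reversal needs p above 1.35/135 = 1.0% to 10.1/135 = 7.5%. With 200 background reports per group and a true 10% fall in intervention counties, the ratio of ratios (true value 0.90) is (180 + 27)/(200 + 13.5) = 0.97 at p = 10%, (180 + 54)/(200 + 27) = 1.03 at 20% and (180 + 108)/(200 + 54) = 1.13 at 40%. The threshold moves with assumptions that the documents cannot settle.

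**The case against.** The strongest reply is that the step from sites to counties is not secure. Enrolment is by site. Participants may live in or around the six counties, any Wisconsin resident using these programmes counts as rural, and Douglas may enrol Minnesota residents (section 4.0; Appendix 1, section 1.5). If WEDSS assigns cases by residence, an unknown share of study reports falls outside the six county rates. This stands, and it prevents a firm size.

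Nor is all study testing additional. One recruitment route at every site is a client already testing there, and testing follows the agency's own procedures. This lowers the yield, though not to zero: peer coupons at intervention sites may reach others, and section 1.3 reports programme clients never tested for HCV.

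The consequence is also limited. Comparisons A to C in Appendix 1, section 1.7 follow participants. Comparison C draws on WEDSS, and section 5.4 links HCV surveillance records to study health-care use. The protocol openly acknowledges bias in a non-randomised design. All of this stands, but neither C nor the linkage names new infection as an outcome, and the two county rows remain listed as effectiveness measures.

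A reader might infer that an effective programme would look harmful on the HCV row. The documents do not support that: it needs yields, incidence and populations that they do not give, and on the assumed inputs the between-group excess is itself within noise.

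**Conclusion.** The point holds as one of interpretability. Study testing feeds two county rates listed as Aim 3 outcomes, unequally by site group and possibly at the year-before point too, and nothing in the plan separates its contribution. Size and net direction are undetermined, because county populations, residence, first-report yield and the placement of T4 are missing.

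On the inputs used here, the HCV row could reliably show neither the bias nor a benefit in the between-group comparison, so it is uninformative about the programme. That result rests on a yield of at most about 20% and on background counts taken from rural catchments, which are not counties. HIV was not calculated, since the documents give no yield; it is probably small, and the HCV row carries most of the concern.

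**What to change.** 1. Label both rows as reported-case rates. Keep them as background surveillance, not as evidence for or against Aim 3. For each county and window, give counts with and without reports from UG3 or UH3 study visits, flagged by study ID, and the number of tests where available. The two counts are bounds, not a correction, because routine testing would have found some of the same people.

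2. Add two descriptive participant-level rows by arm: HCV antibody conversion among those antibody-negative at baseline, and confirmed new HIV among those HIV-negative at baseline. Report numbers tested and missing, with exact intervals. Use person-time or a 3-month cut, because follow-up is shortened in one arm only: "Participants enrolled in the intervention between February 1, 2023 and March 31, 2023 will complete the baseline and 3-month rapid testing only".

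**Cost.** No new visits or specimens: a filter on study reports, test counts, and a small amount of extra analysis. Events will be few. With full follow-up and no effect of navigation, new HCV infections would number 135 person-years × 0.4 × 0.05 = 2.7 to 135 × 0.6 × 0.25 = 20 in the intervention arm, and 67.5 × 0.4 × 0.05 = 1.4 to 67.5 × 0.6 × 0.25 = 10 in controls; losses reduce both. The arms are not randomised, so these rows describe and do not test.

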## 6.0 MEASUREMENT CONSIDERATIONS

### Data analysis for Aim 1.

The research questions under Aim 1 are descriptive rather than hypothesis-driven. The data collected for this Aim will be used in the UG3 phase to describe burden of infectious consequences of injection drug use, and self-reported access to essential prevention services in the selected rural communities. The same data will be used to establish baseline values in the pre/post analyses for the UH3 phase, if selected to proceed, described below (see Section 3.5.4). We will evaluate baseline statistics for participants recruited from the catchment areas associated with each Vivent Health prevention office, to determine if variation exists among rural regions of the state for each of the key variables of interest.

Prevalence estimates and standard errors will be calculated using RDSAT version 7.1. RDS accounts for a source of bias that is especially severe when sampling hard-to-reach groups; namely, that well-connected individuals tend to be over-sampled because many recruitment paths lead to them. RDS draws statistically valid samples of previously unreachable groups by keeping track of who recruited whom and their numbers of contacts eligible for recruitment. The recruitment process mathematical model weights the sample to compensate for non-random recruitment patterns. Based on Markov chain theory and biased network theory, the analysis provides unbiased population estimates and measures of the precision of the estimates.

### Data analysis for Aim 1 DHS Linkage Study on COVID-19 Pandemic Impact Among UG3 Participants.

To estimate the impact of the COVID-19 pandemic on UG3 participants, we will use merged UG3-DHS data to determine several rates and correlates of interest, which are described in detail below.

**COVID-19 outcomes.** To examine risk and protective factors for COVID-19 related outcomes among people who inject drugs, we will use a time-to-event analysis approach (i.e., Kaplan Meier curves and survival analysis with Cox Proportional Hazards regression models) to quantify COVID-19 testing, infection, vaccination, hospitalization, and mortality rates and predictors of these outcomes among participants of our prior study. This will involve excluding our prior study participants who were deceased prior to the start of the US COVID-19 pandemic (March 1, 2020) and calculating person-

time as the number of days from March 1, 2020 through the date of outcome data provided from DHS.

To describe disparities in COVID-19 related outcomes between the general population of Wisconsin and people who inject drugs, we will create a dataset from the linked dataset and the aggregate dataset provided. Each row of data in the analytic dataset will represent the monthly number and person-time estimate of COVID-19 outcomes within people who inject drugs or the general population in Wisconsin, by strata defined by age group, racial-ethnic group, sex, and county. We will graphically summarize average monthly rates of COVID-19 infections, hospitalizations, deaths, tests, and vaccination among the general population in Wisconsin and among people who inject drugs stratified by age group, sex, racial-ethnic group, and county. We will fit Poisson models (or negative binomial if needed due to overdispersion) with each COVID-19 outcome and the following covariates: age group, sex, racial-ethnic group, county, month/year, and an indicator representing whether the row of data corresponds to data from people who inject drugs vs. general population. The coefficient for the indicator variable will be exponentiated to quantify an incidence rate ratio interpretable as the magnitude of disparity between people who inject drugs and the general Wisconsin population for each COVID-19 outcome, adjusted for age, sex, racial-ethnic group, county, and time. We will additionally examine how age group, sex, and racial-ethnic group status modifies the magnitude of disparity by examining interaction terms between the indicator variable and these sociodemographic variables. We may also describe results by county by creating maps. Any rates or counts involving fewer than 5 individuals will be suppressed (i.e., the results will not be viewable on a map), consistent with confidentiality standards of DHS.

*Overdose outcomes.* We will use a time-to-event analysis approach (i.e., Kaplan Meier curves and survival analysis with Cox Proportional Hazards regression models) to quantify fatal overdose rates (from vital records data) and nonfatal overdose rates (from hospitalization data) and predictors of these outcomes among people who inject drugs. This will involve calculating person-time as the number of days from study participation date through the date of outcome data provided from DHS. We will examine sociodemographic and behavioral risk and protective factors (covariate list provided in the appendix) by quantifying hazard ratios. We will also examine whether overdose rates changed pre- and post-COVID-19 by including a time covariate with an interaction term indicative of the period (before March 1, 2020 vs. on/after March 1, 2020). If there are a sufficient number of fatal and nonfatal overdose events per county of residence (>5 events), we will also create maps of overdose rates by county. We may also describe results by county by creating maps. Any rates or counts involving fewer than 5 individuals will be suppressed (i.e., the results will not be viewable on a map), consistent with confidentiality standards of DHS.

*Hepatitis vaccination outcomes.* We will describe vaccination prevalence and use a time-to-event analysis approach (i.e., Kaplan Meier curves and survival analysis with Cox Proportional Hazards regression models) to quantify predictors of hepatitis A and B vaccination among people who inject drugs. We will calculate vaccination prevalence overall (defined as being vaccinated on or before

participation in our prior study). If there are a sufficient number of individuals vaccinated per county of residence (>5 events), we will also create maps of vaccination prevalence by county. For the time to event analysis seeking to understand predictors of vaccination, we will exclude persons vaccinated prior to study enrollment from the predictor analysis to ensure temporality (i.e., that predictors measured during our prior study occurred before the outcome of vaccination). This will involve calculating person-time as the number of days from study participation date through the date of outcome data provided from DHS. We will examine sociodemographic and behavioral risk and protective factors (covariate list provided in the appendix) by quantifying hazard ratios. We may also describe results by county by creating maps. Any rates or counts involving fewer than 5 individuals will be suppressed (i.e., the results will not be viewable on a map), consistent with confidentiality standards of DHS.

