### **1.7 Measuring the impact of the COVID-19 Pandemic on people who inject drugs**

We are now approaching the third year of the COVID-19 pandemic, which collided with a worsening, ongoing overdose epidemic that killed 9,260 people in Wisconsin from 2000-2019 from opioid overdose alone. Consistent with national and state-level trends indicating increases in fatal and nonfatal overdoses, overdose mortality in Wisconsin increased by 28% during 2020 relative to 2019 Unfortunately, provisional 2021 data suggest it will be the deadliest year for drug overdose deaths in Wisconsin and the US. Beyond exacerbations to overdose mortality, prior studies also suggest that COVID-19 itself has disproportionately impacted people who use drugs, and that low vaccine confidence may continue to drive poor outcomes. Studies have shown that people who use drugs are at increased risk for COVID-19 infection, hospitalization, and death. Regarding vaccination, a survey of people who inject drugs in Wisconsin conducted by our team in March-May 2021 indicated that 50% of respondents were hesitant to be vaccinated for COVID-19, consistent with prior studies. Actual COVID-19 vaccination rates and predictors of vaccine uptake have not yet been examined. However, prior studies suggest the potential for considerable under-vaccination for COVID-19 and other infectious diseases that disproportionately impact people who inject drugs (e.g., hepatitis A and B). The extent to which people who inject drugs have accessed other recommended vaccines (i.e., hepatitis A and B) is also unknown, yet has important implications for understanding access to preventive care during the COVID-19 pandemic and potential long-term impacts on liver-related morbidity and mortality.

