## **2.0 STUDY OBJECTIVES**

The overall objective of this project is to leverage our team's successful track record of research, surveillance, and service delivery in Wisconsin to implement an innovative yet widely replicable service delivery model for rural opioid users, which we have named the Community-Based, Client-Centered Prevention Home. The key features of this approach are its implementation in *community-based organizations* rather than traditional clinical settings, its focus on *client-centered service coordination*, and the incorporation of a *mobile health (mHealth) information system* to optimize *quality and comprehensiveness*. Building on our prior success engaging "hidden" populations of rural opioid injectors in research, our specific aims are:

**Aim1:** To estimate the prevalence of HIV, viral hepatitis, and sexually transmitted infections among people who inject drugs to get high, and the availability of essential prevention services, in 6 rural Wisconsin counties.

*Aim 1a: To quantify the impact of the COVID-19 pandemic on participants by summarizing COVID-19, overdose, and vaccination rates and risk and protective factors for these outcomes. We will achieve this aim via linkage of identifiable information from Aim 1 participants with several registries from the Wisconsin Department of Health Services (vital records, hospitalization data, Wisconsin Electronic Disease Surveillance System, Wisconsin Immunization Registry).*

**Aim 2:** To comprehensively assess unmet needs and available resources for the provision of essential prevention services for people who inject drugs to get high in rural communities:

*Aim 2a – We will analyze diverse sources of public health surveillance and administrative data to characterize areas at greatest community-level vulnerability to worsening epidemics of injection drug use.*

*Aim 2b – We will engage key stakeholders from affected communities to identify provider-level characteristics that facilitate person-centered (e.g. relationship-based, culturally sensitive) service delivery.*

*Aim 2c – We will use ethnographic methods and validated questionnaires to describe individual-level barriers to optimal engagement in prevention and treatment services.*

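### For hepatitis A/B vaccination, the linkage analysis gives a pre-pandemic prevalence and an incidence analysis with no split at March 1, 2020, so as written it cannot show a change with the pandemic

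*Combined protocol and SAP*

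**What the plan says.** **Purpose.** Section 2.0 words Aim 1a as "To quantify the impact of the COVID-19 pandemic on participants by summarizing COVID-19, overdose, and vaccination rates", together with their risk and protective factors. Section 1.7 gives the reason for looking at hepatitis A and B vaccines: the extent of uptake is unknown, which "has important implications for understanding access to preventive care during the COVID-19 pandemic" and also bears on later liver disease. The analysis text in Section 6.0 opens with "To estimate the impact of the COVID-19 pandemic on UG3 participants, we will use merged UG3-DHS data". The Study Phases table lists hepatitis A and B vaccination prevalence among the linkage activities.

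**Hepatitis analysis (Section 6.0, hepatitis vaccination outcomes).** "We will calculate vaccination prevalence overall (defined as being vaccinated on or before" continues as "participation in our prior study). If there are a sufficient number of individuals vaccinated per county of residence", and county maps of that prevalence may follow. A time-to-event analysis (Kaplan-Meier and Cox) then looks for predictors of vaccination. It excludes people vaccinated before enrollment and counts person-time from participation to the DHS data date. No period term is given.

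**Overdose analysis (the paragraph just above).** Person-time has the same start and end, but the plan will also "examine whether overdose rates changed pre- and post-COVID-19 by including a time covariate" with an interaction term that separates time before March 1, 2020 from time on or after it.

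**COVID-19 outcomes, including COVID-19 vaccination.** Person-time starts on March 1, 2020, and rates are compared with those of the general Wisconsin population.

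**The concern.** Hepatitis vaccination is the one outcome group in the linkage analysis with neither a pandemic start date nor a pandemic split. The prevalence stops before the pandemic. The incidence analysis crosses March 1, 2020 without marking it.

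What is at stake is whether the study can say anything about hepatitis vaccination before versus during the pandemic. Followed literally, the prevalence and its maps would appear under a pandemic-impact aim while describing the survey period, and no rate during the pandemic would stand beside a rate before it. The plan gives no reason for treating this outcome differently from overdose. Its temporality argument justifies leaving already-vaccinated people out of the predictor model; it does not explain the missing period term.

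**Working it through.** The plan states no sample size, power or event count for this analysis, so there is no figure to reproduce. The check is calendar arithmetic plus one illustration.

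**Inputs from the documents**
- UG3 phase: September 2017 to August 2019 (Study Phases).
- Recruitment goal: from January 2018 (Study Coordination).
- Pandemic start: March 1, 2020 (Section 6.0, COVID-19 outcomes).
- Linkage activity: February 2022 to December 2023 (Study Phases).
- Hepatitis data requested: dates of all A and B doses (Section 5.1.1).

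**Assumption.** No DHS data cut-off is stated. I take it to lie between February 1, 2022 and December 31, 2023.

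**Step 1: where the prevalence date falls**
- Participation on August 31, 2019: 183 days before March 1, 2020.
- Participation on January 1, 2018: 790 days before.

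No participation date within the stated phase reaches the pandemic, so the prevalence as defined contains no pandemic-period vaccination.

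**Step 2: what the time-to-event follow-up mixes**

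Pre-pandemic share = days before March 1, 2020 / (days before + days after).

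| Entry | End | Days before | Days after | Pre-pandemic share |
|---|---|---|---|---|
| Jan 1, 2018 | Feb 1, 2022 | 790 | 702 | 53% |
| Jan 1, 2018 | Dec 31, 2023 | 790 | 1,400 | 36% |
| Aug 31, 2019 | Feb 1, 2022 | 183 | 702 | 21% |
| Aug 31, 2019 | Dec 31, 2023 | 183 | 1,400 | 12% |

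Between 47% and 88% of a participant's potential follow-up is therefore pandemic time. It is present in the analysis but not separated.

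**Step 3: can the pooled rate show a change?**

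Illustration with an assumed pooled rate of 5 per 100 person-years, entry on November 1, 2018 and end on February 1, 2022. This gives a = 1.33 years before and b = 1.92 years after. For a rate ratio r at March 1, 2020, the pre-pandemic rate that yields the pooled rate is 5 × (a + b) / (a + r × b).

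| r | Rate before | Rate after | Pooled rate |
|---|---|---|---|
| 0.5 | 7.10 | 3.55 | 5.0 |
| 1 | 5.00 | 5.00 | 5.0 |
| 2 | 3.14 | 6.29 | 5.0 |

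Three opposite answers to the pandemic question give the same pooled result.

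**Step 4: does the Kaplan-Meier curve fill the gap?** No. Its clock is time since participation, so March 1, 2020 falls anywhere from 183 to 790 days along it, depending on entry. A change at that calendar date is smeared across the curve.

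**The case against.** The strongest reply is that this is a coherent baseline-plus-incidence design. Prevalence at enrollment gives the share already vaccinated; those people are removed, and new vaccination is followed. Aim 1a proceeds by summarizing rates, which can be read descriptively, and the Study Phases table promises only a prevalence. The definition is stated openly and is nowhere called coverage during the pandemic.

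Much of this stands. A survey-date prevalence is a legitimate baseline. It still needs that label, because under the descriptive reading too it summarizes a pre-pandemic state. The incidence half still lacks the one term that would connect it to the pandemic.

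A reader might infer four stronger things that the documents do not support:

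- *That neither hepatitis result touches the pandemic.* The time-to-event analysis runs to the DHS data date, so people vaccinated during the pandemic are events in it.
- *That Aim 1a fails for vaccination in general.* COVID-19 vaccination is counted from March 1, 2020 and compared with the general population.
- *That the data cannot answer the question.* All hepatitis dose dates are requested, so the limit lies in the written analysis.
- *That coverage is understated by a known amount.* The documents give neither an uptake rate after the survey nor the share unvaccinated at survey, so no such figure can be derived.

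It is also tempting to move the county maps to the data date. Linkage uses previous addresses (Section 5.1.1), and Section 9.0 E describes the population as transient. A later map would pair later vaccination status with survey-era residence.

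**Conclusion.** The point holds for hepatitis A/B vaccination only. The prevalence is fixed 183 to 790 days before the plan's pandemic start, given participation between January 2018 and August 2019. The incidence analysis reaches the pandemic but pools it with pre-pandemic time, which makes up 12% to 53% of individual follow-up under the assumed cut-off dates. As written, neither can show whether hepatitis vaccination changed with the pandemic, although Sections 1.7, 2.0 and 6.0 tie the outcome to it.

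The conclusion about the prevalence needs only the documents' dates. The shares depend on the assumed data cut-off, and the 5 per 100 person-years is purely illustrative. This is one outcome group in an add-on linkage study and is readily recovered, so it is a worthwhile correction and not a flaw in the study as a whole. A before/after contrast would show a change at March 2020; it would not by itself prove that the pandemic caused it.

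**What to change.** In the hepatitis paragraph of Section 6.0:

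1. Split each person's follow-up at March 1, 2020. Report hepatitis A and hepatitis B vaccination events, person-years and rates in each period.
2. Add to the Cox model the same before/after period term planned for overdose, as a time-dependent covariate. On the time-since-participation clock, both periods are represented only between 183 and 790 days, so the period-specific rates should be shown beside the hazard ratio.
3. Label the survey-date prevalence as baseline, pre-pandemic coverage. Add prevalence at February 29, 2020 and at the DHS data date, among those alive; deaths are already linked.
4. Keep county maps on the survey-date prevalence, which matches the known residence, or label any later map as by residence at survey.
5. State as a limitation that doses given outside Wisconsin after the survey may be missing from the later prevalence. Note too that doses before participation are requested only where possible, which affects the baseline figure.

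**Cost.** SAP wording and a little programming. Section 5.1.1 already requests all dose dates and the vital records linkage, so no new data request is needed.
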